1.2 RATIONALE FOR STUDY

1.2.1 Research Hypothesis

We hypothesise that a more liberal postoperative transfusion strategy will reduce death and major cardiovascular complications in people with hip fracture and anaemia, compared with currently recommended more restrictive transfusion strategies. We hypothesise that a more liberal blood transfusion practice will be cost-effective in this population.

1.2.2 Benefits of the study

The evidence base for best practice in this group is uncertain, especially in the presence of cardiovascular disease, and guidelines are inconsistent and not followed reliably, leading to substantial variation in clinical practice. Better evidence to guide the clinical and cost-effectiveness of RBC transfusion in this group will reduce variation, improve clinical outcomes, and generate economic and efficiency benefits for the NHS in one of its largest emergency populations. Evidence-based personalised anaemia management could substantially improve people's health, reduce healthcare costs, and relieve unscheduled care bed pressures. The results of the study may contribute to guidance for clinicians via NICE and HIS/SIGN for management of hip fracture, and dissemination of results to improve clinical care via clinical networks. The findings of this research may also inform blood management of other high risk groups undergoing surgery.

CR007-T02 v0.5 Page **18** of **69**

IRAS 299977/308830

Version 5.0 26Jun2024

1.2.3 Study treatment under investigation: liberal vs restrictive blood transfusion strategy

The intervention being investigated is postoperative blood transfusion using different haemoglobin triggers.

The blood product will be standard issue RBCs produced by transfusion services and issued according to routine clinical practice. The treatment arms of this study will be "liberal" and "restrictive". The "liberal" group will be transfused at a threshold of Hb 90 g.L⁻¹ or less (post-transfusion target Hb 90-110 g.L⁻¹) from randomisation until acute hospital discharge or 30 days post-randomisation, whichever is sooner. This is more liberal than current guidance but consistent with practice and beliefs of many clinicians in this population for the reasons which have been outlined earlier. This practice is like that recommended by the AoA working group for hip fracture and included in the AAGBI hip fracture guideline.

The "restrictive" transfusion group will be transfused at a threshold of 75 g.L⁻¹ or less (posttransfusion target Hb of 75-90 g.L⁻¹) from randomisation until acute hospital discharge or 30 days, whichever is sooner. As noted above, NICE guidance suggests a transfusion trigger of 70 g.L⁻¹ or less and that Hb should be maintained in the 70-90 g.L⁻¹ range, however other available guidance suggests a higher trigger of 80 g.L⁻¹. In our pilot study some clinicians were unwilling to wait until Hb fell to below 70 g.L⁻¹ before prescribing a blood transfusion. Therefore, to best represent acceptable current practice, and improve compliance in this arm, a trigger of 75 g.L⁻¹ or less was chosen to maintain optimal compliance while ensuring that participants' Hb remained within the desired range. This practice is therefore like that recommended by most generic transfusion-specific guidelines.

In both groups single unit RBC transfusions will be given followed by Hb reassessment, consistent with best practice guidelines. (29, 31)

1.2.4 Desirable study outcome

In people with hip fracture, we estimate 30-day all-cause mortality will be 7%, rates of MACE will be 10%, and rate of new MINS will be 20%. These rates may be higher in the anaemic populations being included in this study. We consider an absolute risk reduction (ARR) of 5% in the combined primary outcome of MACE, new MINS and death to be a realistic meaningful effect size that would change clinical practice (33% Relative RR). This would represent a number needed to treat (NNT) of 20 for every patient receiving liberal transfusion to avoid a death and/or MACE outcome compared to the restrictive group.

IRAS 299977/308830

Version 5.0 26Jun2024

STUDY OBJECTIVES

1.3 OBJECTIVES

1.3.1 Primary Objective

To determine if a liberal postoperative transfusion strategy (transfused at a threshold of Hb 90 g.L⁻¹ or less) will reduce death and major cardiovascular complications, compared with practice recommended in many transfusion guidelines (restrictive transfusion strategy), in people with hip fracture and anaemia.

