1.4 ENDPOINTS

1.4.1 Primary Endpoint

The primary outcome will be death OR major adverse cardiac events (MACE) OR new myocardial injury after non cardiac surgery (new MINS) within 30 days of randomisation.

MACE will be defined as any combination of the following:

- Myocardial Infarction: Diagnosed using the 4th Universal Definitions for MI(14)
- New Arrhythmia: ECG confirmed arrhythmia resulting in a fall in mean arterial pressure of >20% and requiring pharmacological or cardioversion treatment.
- Cardiac or respiratory arrest: Resuscitation Council UK definitions
- Cardiogenic pulmonary oedema.

New MINS will be defined as : new elevated postoperative troponin above the upper reference limit (URL) with a rise/fall pattern indicative of acute myocardial injury occurring in the first 30 days (and typically within 72 h) after surgery; attributable to a presumed ischemic mechanism,

IRAS 299977/308830

Version 5.0 26Jun2024

clinical symptoms masked by sedation or analgesia in the perioperative setting, ischemic features (e.g. ECG, echocardiographic changes) not required.

To maximize validity and consistency, all participants will have troponin measured at randomisation (baseline), and then twice more in days 1 to 5, ideally on the 1st and 3rd calendar days after randomisation with all samples being at least 24h apart from each other, and 12-lead ECGs will be performed at baseline and repeated once in days 2 - 5. The primary outcome will be determined by an expert adjudication team blinded from group allocation.

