To address the possibility that any component of the primary outcome (particularly Atrial fibrillation (AF) or new MINS) is much more prevalent in the trial than expected and dominates the primary composite outcome, we propose the following: all the individual components of MACE and new MINS will be reported as secondary outcomes and an a priori sensitivity analysis is undertaken with the AF and new MINS components of the primary outcome removed. This will be pre-specified in the statistical analysis plan when developed and proposed as a secondary analysis.

Secondary outcomes will be analysed using logistic regression for binary outcomes and linear regression for normally distributed continuous outcomes. Continuous outcomes that are not normally distributed will be analysed using appropriate non-parametric techniques. Time to event data will be analysed using an appropriate survival model (e.g., Cox proportional hazards).

Pre-specified sub-group analyses will explore effects in relation to gender, age (<80 vs. \geq 80 years), presence of pre-existing CVD and use of anticoagulant and antiplatelet drugs. These will be analysed as per the primary outcome but including a covariate*treatment interaction.

No interim analysis is planned.

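### The hypothesis, primary objective and NNT of 20 still refer to death and major cardiovascular events, while the primary outcome and its 5-point reduction also count new MINS

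*Protocol*

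**What the plan says.** The hypothesis in section 1.2.1 is that "a more liberal postoperative transfusion strategy will reduce death and major cardiovascular complications". The primary objective in 1.3.1 is to find out whether the liberal strategy "will reduce death and major cardiovascular complications, compared with practice recommended in many transfusion guidelines (restrictive transfusion strategy"). Neither names new MINS.

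Section 1.4.1 defines the outcome: "The primary outcome will be death OR major adverse cardiac events (MACE) OR new myocardial injury after non cardiac surgery (new MINS) within 30 days", counted from randomisation. MACE is a list of four items (infarction, arrhythmia, arrest, pulmonary oedema) that does not contain MINS. New MINS has its own definition, based on troponin, with "clinical symptoms masked by sedation or analgesia in the perioperative setting, ischemic features (e.g. ECG, echocardiographic changes) not required". The ordinal scale in 9.1 and 9.2 places new MINS without death or MACE at rank 2 of 6, below MACE at rank 3.

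Section 1.2.4 sets a 5-point absolute risk reduction on the combination of MACE, new MINS and death. Its next sentence says the NNT of 20 is to "avoid a death and/or MACE outcome compared to the restrictive group". Section 9.1 repeats this.

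Section 9.1 acknowledges that less severe components may dominate the composite, and adopts the ranking for that reason. Section 9.2 adds separate component reporting and an a priori sensitivity analysis without AF and new MINS, in case any component "is much more prevalent in the trial than expected and dominates the primary composite outcome".

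**The concern.** The claim to be made and the outcome to be tested are not the same. The rank test is the primary analysis, so a significant result will be read against the objective in 1.3.1. If the difference came mainly from rank 2, the trial would have shown less troponin-defined injury, and the objective as worded would credit it with fewer deaths and major cardiovascular events.

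The NNT has the same fault in numerical form. An effect set on one event is described as avoiding a different, rarer one. A guideline reader would take from the protocol that 20 patients need liberal transfusion to prevent one death or MACE, and the plan's own rates do not give that.

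**Working it through.** **Inputs.** Death 7%, MACE 10%, new MINS 20% (9.1); MACE including death 10% (9.1); primary outcome 15% (3.1); absolute reduction 5 points (1.2.4, 3.1, 9.1); planned relative reduction 30%, 507 evaluable per arm, two-sided 5% (9.1).

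**1. The plan's own figures.** NNT = 1/0.05 = 20, and 5/15 = 33%. Both reproduce, but the 5 points are defined on the composite with new MINS.

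**2. NNT for death or MACE at the stated 10%.**
- 30% relative reduction: 10% to 7%, NNT = 1/0.03 = 33.
- 33% relative reduction: 10% to 6.67%, NNT = 30.
- An NNT of 20 would need 10% to 5%, a 50% relative reduction.

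**3. Power for death or MACE as a binary outcome, 10% v 7%, 507 per arm.** With mean proportion 0.085:
- power = Φ[(0.03√507 − 1.96√(2×0.085×0.915)) / √(0.10×0.90 + 0.07×0.93)]
- = Φ[(0.6755 − 0.7730)/0.3938] = Φ(−0.248) = 40%.
- 90% power would need 1,814 per arm. At the 33% reduction, power at 507 per arm is 48%.

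**4. Share of events that are new MINS only.** This depends on overlap, which the protocol does not give.
- Disjoint, MACE including death 10%: 20/30 = 67%.
- Disjoint, death 7% and MACE 10% added: 20/37 = 54%.
- With overlap the share falls. If 5 of the 20 points also had death or MACE (10% base), it is 15/25 = 60%.

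**5. Primary rank test when only new MINS changes.** Assumed control distribution over ranks 1 to 6: 70/20/3/2/2/3% (10% base) or 63/20/10/2/2/3% (17% base). The liberal arm moves a proportion δ from rank 2 to rank 1, and ranks 3 to 6 stay fixed. Let θ be the probability that a control patient ranks worse than a liberal patient, counting ties as half.
- θ − ½ = δ(p1 + p2)/2
- variance = (2n + 1)(1 − Σp̄³)/(12n²), where p̄ is the mean category proportion
- Example, 20% to 15%, 10% base: θ − ½ = 0.05×0.90/2 = 0.0225; 1 − Σp̄³ = 0.6135; SE = √(1015×0.6135/(12×507²)) = 0.0142; z = 1.58; power = Φ(1.58 − 1.96) = 35%. Simulation gives 36%.

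| New MINS, control to liberal | 10% base | 17% base |
|---|---|---|
| 20% to 15% | 36% | 27% |
| 20% to 14% | 48% | 37% |
| 20% to 12% | 73% | 59% |
| 20% to 10% | 91% | 79% |

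Simulation of the tie-corrected test agrees to about a percentage point. The split within ranks 3 to 6 hardly matters, because θ depends only on p1 + p2. If overlap leaves only 15% at rank 2 (10% base), a 30% cut in that rank is significant 33% of the time instead of 48%.

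**6. The reverse case.** Cut ranks 3 to 6 by 30% and leave rank 2 alone. With q the death-or-MACE rate, θ − ½ = 0.3q(1 − p1/2 − q/2).
- 10% base: 0.03×0.60 = 0.018, detected about 24% to 25% of the time.
- 17% base: 0.051×0.60 = 0.0306, detected about 52% of the time.

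**The case against.** **Any composite can be positive through one component.** The protocol gives its reason for including MINS: section 1.1.1 describes an independent, strong association with short- and long-term mortality. The outcome is stated openly in the abstract and 1.4.1. This stands, and the point is not an argument against counting new MINS.

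**The objective's phrase is broader than MACE and undefined, so it is loose more than false.** This stands in part. But the protocol nowhere calls MINS major, defines it apart from MACE and ranks it lower. The defence does not reach the NNT sentences, which name MACE.

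**Safeguards exist.** Ranking was adopted because of the dominance risk, mortality and the components are secondary endpoints, and the analysis without AF and new MINS is a priori. A reader might infer from 9.2 that this analysis runs only if MINS proves unexpectedly frequent. The text gives that as the motive and sets no trigger. What the safeguards do not do is align the stated claim with the test. No conclusion on death or MACE is tied to them.

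**A reader might also infer that the trial would probably be positive on new MINS alone, or that two thirds of events are certain to be MINS.** The documents support neither. If the protocol's own 5 points fell wholly on MINS, the test would be significant 27% to 36% of the time. The 79% to 91% figures need MINS halved with no change in infarction, and the protocol gives no basis for expecting that. The two-thirds share assumes no overlap, whereas 9.1 expects components to coincide in some participants.

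**Conclusion.** The protocol contradicts itself on what the NNT of 20 refers to, and its hypothesis and objective do not match its primary outcome. The NNT of 20 holds only for the composite with new MINS. For death or MACE at the stated 10%, the planned 30% reduction gives an NNT of about 33 and about 40% power. This part needs no assumed category split.

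On the size of the risk, new MINS would supply 54% to 67% of events if it does not overlap with death or MACE, and less if it does. With death and MACE unchanged, the chance of a significant primary test runs from 27% to 36% (MINS to 15%) up to 79% to 91% (MINS to 10%). A 30% cut in death or MACE alone is detected about 24% to 52% of the time. These ranges rest on the assumed splits; the assumed 10% base also carries 22% MINS in all (ranks 2 and 5), slightly above the stated 20%. They are enough to show that a positive test need not support the objective as worded. They do not show that a false claim is likely, or that the dominance risk was overlooked.

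**What to change.** - In 1.2.1 and 1.3.1, state the hypothesis and objective on the ranked outcome of death, MACE or new MINS.
- In 1.2.4 and 9.1, say that the event avoided in the NNT of 20 is the composite including new MINS. If an NNT for death or MACE is wanted, give it separately with its own rate and reduction.
- In 9.2, state that any conclusion about death and MACE rests on the already planned analyses without new MINS, and not on the primary rank test alone. The planned sensitivity analysis removes AF as well, so say whether AF is kept when the claim concerns MACE as defined in 1.4.1.

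The cost is protocol wording carried into the SAP. No new data, patients or tests are needed. The downside is a less favourable headline claim.

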1.3.2 Secondary Objectives

Our secondary objective is to determine whether a liberal postoperative transfusion strategy will improve quality of life at 120 days and reduce costs in people with hip fracture and anaemia, compared with usual care.

At 30 days we will assess the impact of a liberal postoperative transfusion strategy on: all-cause mortality; Myocardial Injury (defined as detectable troponin release above the Upper Reference Limit (URL)); individual MACE components; new MINS; other complications (including acute kidney injury [AKI], infection, delirium); proportion transfused; volume of blood transfused; discharge destination; hospital length of stay, HRQoL (EQ-5D-5L)

At 120 days we will assess the impact of a liberal postoperative transfusion strategy on: allcause mortality; secondary care costs; unplanned hospital readmissions within 120 days; mobility (as defined by NHFD dataset); residential status (as defined by NHFD); HrQoL (EQ-5D-5L).

1.4 ENDPOINTS

1.4.1 Primary Endpoint

The primary outcome will be death OR major adverse cardiac events (MACE) OR new myocardial injury after non cardiac surgery (new MINS) within 30 days of randomisation.

MACE will be defined as any combination of the following:

- Myocardial Infarction: Diagnosed using the 4th Universal Definitions for MI(14)
- New Arrhythmia: ECG confirmed arrhythmia resulting in a fall in mean arterial pressure of >20% and requiring pharmacological or cardioversion treatment.
- Cardiac or respiratory arrest: Resuscitation Council UK definitions
- Cardiogenic pulmonary oedema.

New MINS will be defined as : new elevated postoperative troponin above the upper reference limit (URL) with a rise/fall pattern indicative of acute myocardial injury occurring in the first 30 days (and typically within 72 h) after surgery; attributable to a presumed ischemic mechanism,

IRAS 299977/308830

Version 5.0 26Jun2024

clinical symptoms masked by sedation or analgesia in the perioperative setting, ischemic features (e.g. ECG, echocardiographic changes) not required.

To maximize validity and consistency, all participants will have troponin measured at randomisation (baseline), and then twice more in days 1 to 5, ideally on the 1st and 3rd calendar days after randomisation with all samples being at least 24h apart from each other, and 12-lead ECGs will be performed at baseline and repeated once in days 2 - 5. The primary outcome will be determined by an expert adjudication team blinded from group allocation.

1.4.2 Secondary Endpoints

Secondary outcomes at 30 days are as follows:

- 1. All-cause mortality
- 2. New Myocardial Injury post-randomisation (New MINS)
- 3. Individual MACE components (including type of arrhythmia)
- 4. Complications (including AKI, infection, delirium)
- 5. Proportion of participants transfused; volume of blood transfused per patient
- 6. Discharge destination (home, other hospital, nursing home, other)
- 7. Acute hospital length of stay
- 8. ED-5D-5L

Additional secondary outcomes at 120 days are as follows:

- 1. All cause mortality
- 2. Secondary care costs
- 3. Unplanned hospital readmissions
- 4. Mobility (as defined by NHFD or SHFA dataset
- 5. Residential status (as defined by NHFD or SHFA dataset)
- 6. EQ-5D-5L
- 7. Health services resource use

Clinical outcomes will be measured until acute hospital discharge or 30 days post randomisation whichever is soonest. Death, readmission, mobility, residential status, quality of life and resource use will be measured at 120 days post-randomisation.

2 STUDY DESIGN

2.1 STUDY DESIGN

RESULT-Hip is a multicentre, parallel-group randomised controlled clinical and cost effectiveness trial with internal pilot of two transfusion strategies in people with hip fracture. Participants will be allocated to each treatment arm using a web-based allocation system at random in a 1:1 ratio.

IRAS 299977/308830

Version 5.0 26Jun2024

2.1.1 Internal pilot

In a 6-month internal pilot we will aim to open at least 10 sites and randomise at least 150 participants. We will collect data on screening, patient/clinician refusal, and undertake telephone interviews with sites to discuss recruitment and trial fidelity. We will also hold focus groups with patients and clinicians to examine barriers to recruitment and protocol compliance and ensure best practice.

2.1.2 **Process Evaluation**

We will include a process evaluation (PE) of the internal pilot study, consistent with MRC guidance,(32) to explore the processes involved in delivering the intervention and any facilitators or barriers to recruitment. Our objectives are to establish the extent to which the intervention is implemented as intended during the internal pilot across different sites; to ascertain how feasible and acceptable the intervention is to clinical staff across different sites; to identify any facilitators and barriers to recruitment.

The methods used to conduct the PE of the internal pilot will be:

- During site initiation: At site initiation visits we will identify key research staff, collect baseline data on context and establish acceptability of the study protocol. These data will inform feasibility and any changes required to maximise recruitment and fidelity of the trial protocol for the main study as well as developing relationships with sites involved in the internal pilot.
- During the internal pilot: All sites in the internal pilot will be invited to participate in individual telephone interviews. The interviews will be undertaken with a member(s) of the research team which may include the PI, an investigator or a research nurse/ co-ordinator and a clinician from each site. Purposive sampling will be used to recruit a range of participants according to grade, profession and role in the research or clinical teams.

We will use a framework approach to analyse the qualitative data as this offers a systematic and flexible approach. Themes identified *a priori* alongside those generated through the iterative process of collecting and analysing data will lead to the development of the final analytical framework. Trustworthiness criteria will be considered at each stage to ensure the quality of the process evaluation. The researcher will keep an audit trail of decisions around sampling and analysis to ensure confirmability and dependability, thick description of the process will support transferability, and credibility will be achieved through informal member checking with participants during interview and independent coding of a sample of interview data.

IRAS 299977/308830

Version 5.0 26Jun2024

2.1.3 Trial Progression

Trial progression beyond the internal pilot phase will be based on TSC, DMC and HTA review of the PE and the following metrics.

"Red/Amber/Green" trial progression criteria:

- sites open/recruiting (<5 red; 5-10 amber; >10 green).
- Participants recruited (<75 red; 75-130 amber; >130 green).
- protocol adherence: adherence defined as transfusion only after checking Hb and transfusion consistent with predefined haemoglobin trigger. Based on deviations/violations we will use the following system: <70% red; 70-90% amber; >90% green).
- Recruitment rate/site/month open (<2.2 red; 2.2-3.7 amber; >3.7 green)

2.2 CENTRES

Most acute hospital trusts manage people with hip fracture as part of their usual emergency workload: this makes many UK hospitals available as potential recruiting sites.

We intend to recruit 25 - 30 sites to participate in this trial. The average trauma unit treats 400 people with hip fracture per year, but some high-volume centres treat over 800.

It is planned that 10 pilot sites will open at a rate of 2 sites per month and will aim to recruit, on average, 4.3 participants per site per month open. Following the 6-month internal pilot, it is anticipated sites will continue to open at a rate of 1-2 sites per month until the full complement of 25 - 30 sites is achieved Recruitment rates during this period are estimated at 1.3-1.6 patients per site per month open. In total, there will be 51 months of recruitment, cumulating to around 900 centre-months of available recruitment time.

